13.3 Local Tolerability Scale (LTS) Scores

Local tolerability scale scores will be summarized with frequency counts and percent by treatment and visit for subject (or caregiver) overall assessment for burning/stinging and for itching (scores from 0=None to 4=Strong/Severe) and Investigator overall assessment for dryness, erythema, and peeling (scores from 0=No irritation to 4=Very Severe) separately. Additionally, observed values and change from baseline will be summarized by treatment and visit.

Local tolerability scale scores and change from Baseline scores at the sensitive areas (face, neck, skin folds, axilla, inframammary, anal crux, and genitalia) where study drug is applied will be summarized by visit, area, and treatment group for Investigator overall assessment, as well as listed by subject and anatomical site.

13.4 Clinical Laboratory Evaluation

Laboratory values will be classified as normal, low, or high based on normal ranges supplied by the laboratory. Changes from baseline in abnormality status will be summarized using shift tables by visit.

For quantitative laboratory measures, observed values and changes from baseline will be summarized descriptively by visit and treatment group.

13.5 Vital Signs

Vital signs (systolic and diastolic blood pressure [SBP and DBP], pulse rate, and body temperature) will be summarized using descriptive statistics at baseline and at each post-baseline time point. Changes from baseline will also be summarized.

Vital sign values in adults (≥18 yrs) will be classified as normal, low, high, based on reference ranges as per below. Subjects with markedly abnormal changes will be listed and tabulated separately.

	Absolute Values			Change (Absolute) from Baseline		
	Low	Normal	High	Abnormal Change	Markedly Abnormal Change	
SBP	<90 mmHg	90-140 mmHg	>140 mmHg	≥20 mmHg	≥40 mmHg	
DBP	<50 mmHg	50-90 mmHg	>90 mmHg	≥10 mmHg	≥20 mmHg	
Pulse	<50 bpm	50-100 bpm	>100 bpm	≥10 bpm	≥30 bpm	

Blood pressure in children (<18 yrs) will be classified as normal or elevated based on reference ranges as per Table below. Subjects with markedly abnormal changes will be listed and tabulated separately.

		Absolute Values		Change (Absolute) from Baseline	
Age		Normal	Elevated	Abnormal Change	Markedly Abnormal
					Change
2-6 yrs old	SBP	<105 mmHg	≥105 mmHg	≥20 mmHg	≥30 mmHg
	DBP	<67 mmHg	≥67 mmHg	≥10 mmHg	≥20 mmHg
7-11 yrs old	SBP	<110 mmHg	≥110 mmHg	≥20 mmHg	≥30 mmHg
	DBP	<74 mmHg	≥74 mmHg	≥10 mmHg	≥20 mmHg
12-17 yrs old	SBP	<120 mmHg	≥120 mmHg	≥20 mmHg	≥30 mmHg
	DBP	<80 mmHg	≥80 mmHg	≥10 mmHg	≥20 mmHg

Pulse in children (<18 yrs) will be classified as low, normal, or high based on reference ranges as per Table below. Subjects with abnormal (low or high) values will be listed and tabulated separately.

	Absolute Values				
	Low	Normal	High		
2-10 yrs old	<60 bpm	60-140 bpm	>140 bpm		
11-17 yrs old	<50 bpm	50-100 bpm	>100 bpm		

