4.1 Type and Number of Subjects

Approximately 400 adult and pediatric subjects ages 2 years and above with AD will be enrolled in the study at approximately 60 study sites in the US and Canada. A minimum of approximately 15% of subjects will be enrolled into each of the following age groups: 2-6 years, 7-11 years, 12-17 years, 18 years and above. Adults 18 years and above will comprise a maximum of 20% of enrolled subjects.

Protocol violations from inclusion and exclusion criteria are prohibited because ineligible study subjects can potentially jeopardize the scientific integrity of the study, regulatory acceptability, or subject safety. Therefore, adherence to the criteria as specified in the protocol is essential.

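### SAP 13.5 gives pediatric blood pressure no low category, so any low reading in a subject under 18 is classified as 'Normal' and cannot be counted by arm

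*SAP*

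**What the plan says.** SAP 13.5 sets out three classification schemes for vital signs.

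- **Adults, SBP, DBP and pulse:** "Vital sign values in adults (≥18 yrs) will be classified as normal, low, high, based on reference ranges as per below". Low is SBP below 90 mmHg, DBP below 50 mmHg or pulse below 50 bpm.
- **Children, pulse:** "Pulse in children (<18 yrs) will be classified as low, normal, or high based on reference ranges as per Table below". Children with a low or a high pulse get their own listing and table.
- **Children, blood pressure:** "Blood pressure in children (<18 yrs) will be classified as normal or elevated based on reference ranges as per Table below". Normal SBP is below 105, 110 or 120 mmHg, and normal DBP below 67, 74 or 80 mmHg, at ages 2-6, 7-11 and 12-17 years. Values at or above these limits are 'Elevated'. No lower limit is given.

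The pediatric blood pressure table also has two tiers of change from baseline: 'Abnormal' (SBP 20 mmHg or more, DBP 10 mmHg or more) and 'Markedly Abnormal' (SBP 30 mmHg or more, DBP 20 mmHg or more). Only the second tier has a stated output: "Subjects with markedly abnormal changes will be listed and tabulated separately".

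Vital signs also "will be summarized using descriptive statistics at baseline and at each post-baseline time point", and changes from baseline are summarized.

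On population, Protocol 4.1 says "Approximately 400 adult and pediatric subjects ages 2 years and above with AD will be enrolled" and "Adults 18 years and above will comprise a maximum of 20% of enrolled subjects".

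**The concern.** Change from baseline in vital signs is a listed safety endpoint (Protocol 2). A category called 'Normal' with no floor does not mean normal; it means not elevated. A reader of the categorical summary would take it to cover both directions, because the adult blood pressure and pediatric pulse summaries beside it do.

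The gap falls on the larger part of the trial: the group with a two-sided blood pressure scheme is the one the protocol caps. What is at stake is the ability to compare tapinarof with vehicle on the number of children with low blood pressure at each visit. No formal test or efficacy conclusion is involved, since SAP 13 makes no formal safety comparisons.

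Protocol 10.4.3 adds a little weight. It classifies laboratory values as normal, low or high, then says vital signs will be handled in a similar way, and SAP 14 declares no change from the protocol's analyses. 'Similar' may mean only the descriptive summaries, so this is supporting context and not a proven contradiction.

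**Working it through.** **1. Share of the trial affected.** Inputs from Protocol 4.1: about 400 subjects; adults at most 20%, with a minimum of about 15%.

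- Adults at the cap: children = 1 − 0.20 = 0.80; 0.80 × 400 = 320.
- Adults at the minimum: children = 1 − 0.15 = 0.85; 0.85 × 400 = 340.

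So about 320 to 340 subjects fall under the one-sided range. This is planned enrolment; the safety population could differ slightly.

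**2. Applying the SAP 13.5 limits to test readings.** The readings are illustrative. The adult limits are used only to show the asymmetry, not as pediatric limits.

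| Reading (SBP/DBP, mmHg) | 2-6 yrs (<105/<67) | 7-11 yrs (<110/<74) | 12-17 yrs (<120/<80) | Adult table (low: <90/<50) |
|---|---|---|---|---|
| 89/49 | Normal/Normal | Normal/Normal | Normal/Normal | Low/Low |
| 70/40 | Normal/Normal | Normal/Normal | Normal/Normal | Low/Low |
| 50/25 | Normal/Normal | Normal/Normal | Normal/Normal | Low/Low |

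With no lower bound, no reading, however small, can leave 'Normal' on the low side.

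**3. Whether the change criteria fill the gap.** Take an invented SBP fall from 90 to 62 mmHg in a 5-year-old.

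- Fall: 90 − 62 = 28 mmHg.
- 28 ≥ 20, so it meets the 'Abnormal Change' tier.
- 28 < 30, so on SBP alone it misses the 'Markedly Abnormal' tier and the separate listing and table. A DBP change of 20 mmHg or more would bring the child in independently.
- Absolute value: 62 < 105, so 'Normal'.

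A child who is low at baseline and stays there has a change near 0 and meets neither tier.

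The tiers state no direction. If 'absolute' means magnitude, rises and falls are pooled and the table does not isolate low values. If it means signed change in mmHg, falls are not captured at all.

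**The case against.** The strongest reply is that low readings are visible elsewhere, and much of it stands.

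- Protocol 10.1 and 10.4.3 and SAP 6 require safety data to be listed by subject.
- The descriptive statistics include minimums by treatment and visit, so an extreme low value or a downward shift in the mean would show.
- Protocol 8.1.1 makes clinically significant vital sign abnormalities adverse events, and Protocol 8.2.1.2.5 sends significant changes that put a subject at risk to the Medical Monitor.
- The 28 mmHg fall above is flagged by the table's own first tier.

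A reader might therefore go too far in inferring that such a child is not listed, or that the safety analysis cannot show low blood pressure. The documents do not support either: the child is missing only from the separate listing of markedly abnormal changes. Nor can one infer that the pediatric normal rate will sit near 100% as an artefact. That rate is 100% minus the elevated rate, and the documents do not predict it.

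Three further limits are fair. The visible text names contact dermatitis, folliculitis and headache as events of special interest and does not point to low blood pressure; the risk section is redacted, so a reason for an elevated-only scheme may exist unseen. The documents give no pediatric lower limit, so calling any particular reading low needs an outside reference. And SAP 13.5 says values are classified, while the table shells are not in the text reviewed, so the final display cannot be checked.

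What the reply does not supply is a count. A minimum is one value per arm and visit, SAP 13.5 does not say it is shown by age group, a listing is not a comparison, and the adverse event route depends on investigator judgement.

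**Conclusion.** The point holds as a minor one. Followed as written, SAP 13.5 classifies every low SBP or DBP in a subject under 18 as 'Normal', for at least 80% of planned enrolment (about 320 of 400). A categorical summary built on that rule cannot count low pediatric blood pressure by arm. A value that is low from baseline, or is reached by a fall below the markedly abnormal thresholds, is counted only as 'Normal' in the absolute-value classification and is not promised any separate output.

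This rests on two assumptions: the adult cap is kept, and the summary uses the SAP's categories as written. It does not depend on where a pediatric lower limit would be set. It concerns one descriptive safety summary and leaves efficacy testing and sample size unchanged.

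**What to change.** In SAP 13.5, add a low category for SBP and DBP to each pediatric age row (2-6, 7-11 and 12-17 years), with limits set by the sponsor's medical team. Tabulate low, normal and elevated by visit and arm, and list children with low values, as the section already does for pediatric pulse.

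If the sponsor prefers not to set pediatric lower limits, relabel 'Normal' as 'Not elevated' and give the reason for leaving out the low side. That corrects the label but still gives no count of low values.

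The cost is SAP and table-shell wording, one added column and one listing. The readings are already collected. Making the change before database lock keeps the analysis pre-specified under SAP 6.

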13.6 Physical Examination

Physical examination results will be included in data listings only.

13.7 Electrocardiogram

The ECG data analysis will be conducted based on methodology recommended in the ICH E14 guideline (International Council for Harmonisation, 2005)⁹.

Overall interpretation results for ECG will be summarized using shift tables (Normal, Abnormal Not Clinically Significant, Abnormal Clinically Significant) comparing baseline to end of treatment (Week 8). Descriptive statistics at baseline and at each post-baseline time point as well as changes from baseline will be summarized for each ECG parameter.

In addition, a categorical summary of abnormal corrected QT interval (QTc) values will be presented. At each time point, the number of subjects with QTc according to Fridericia's formula, QTcF and QTc according to Bazett's formula (QTcB) values of >450 ms, >480 ms, and >500 ms will be presented. At each post-baseline time point, the number of subjects with change from baseline values in QTcF and QTcB of >30 ms and >60 ms will be presented.

14. CHANGES TO PROTOCOL-SPECIFIED ANALYSES

Not applicable. There are no changes to the protocol-specified analyses.

16. APPENDICES

APPENDIX A: PRESENTATION OF DATA AND PROGRAMMING SPECIFICATIONS

General

- Specialized text styles, such as bold, italics, borders, shading, and superscripted and subscripted text will not be used in tables, figures, and data listings unless they add significant value to the table, figure, or data listing.
- Only standard keyboard characters are to be used in tables and data listings.
- Special characters, such as nonprintable control characters, printer-specific, or font-specific characters, will not be used on a table, figure, or data listing.
- Hexadecimal character representations are allowed (e.g., μ , \square , β).
- All footnotes will be left justified and at the bottom of a page. Footnotes must be used sparingly and must add value to the table, figure, or data listing.

Tables

- Means and medians will be presented to 1 more decimal place than the raw data. Standard deviations will be presented to 2 more decimal places than the raw data. Minimums and maximums will be reported with the same number of decimal places as the raw data. If raw data has more than 2 decimal places, the same rule will be applied as the raw data with 2 decimal places. For MI tables with categorical endpoint, mean success %, median, min and max will be presented to 1 decimal place. Standard error will be presented to 2 decimal places.
- Percentages will be presented to the tenths place.
- For frequency counts of categorical variables, categories whose counts are zero will be
 displayed for the sake of completeness. For example, if none of the subjects discontinue
 due to "lost to follow-up," this reason will be included in the table with a count of 0.
 Categories with zero counts will have zero percentages displayed. Results of one hundred
 percentages and zero percentages will have the same representation in tables as other
 percentages.
- Lower and upper CI values must be presented to 1 decimal place more than the raw/derived data (i.e., to the same number of decimal places as the mean).
- Percentiles (e.g., 25%, 75%) must be presented to 1 decimal place more than the raw/derived data.
- For all inferential analyses, *P* values will be rounded to 4 decimal places (or at the highest level of precision) with a leading zero (0.0001). *P* values less than 0.0001 will be presented as "<0.0001."
- The last footnotes will be
 - "Source: xxx", where xxx indicates the source **table number**(s) if applicable (in case aggregated results like mean or median are plotted), or the source listing(s) (in case individual responses are plotted), and/or source dataset(s) (e.g., ADaM).

- "PROGRAM SOURCE: ...\\xx.sas, RUN DATE: DDMMYY hh:mm".

Figures

- Legends will be used for all figures with more than 1 variable or item displayed. Treatment group sizes (n=xx) will be included, as appropriate.
- Figures will be in black and white but can be in color to add value to the clarity and readability of a figure. Lines must be wide enough to see the line after being copied.
- The last footnotes will be
 - "Source: xxx", where xxx indicates the source listing number(s) and/or source dataset(s) (e.g., ADaM).
 - "PROGRAM SOURCE: ...\\xx.sas, RUN DATE: DDMMYY hh:mm".

Listings

- If not otherwise specified, all data listings will be sorted by treatment, subject number, visit, and date/time, as appropriate.
- All date values will be presented in a SAS date (e.g., YYYY-MM-DD) format.
- All observed time values will be presented using a 24-hour clock HH:MM:SS format (e.g., 01:35:45 or 11:26). Seconds will only be reported if they were measured as part of the study.
- The last footnote will be
 - "PROGRAM SOURCE: ...\\xx.sas, RUN DATE: DDMMYY hh:mm".

Standard Calculations

Variables requiring calculation will be derived using the following formulas:

• **Days** – A duration expressed in days between 1 date (date1) and another later date (date2) is calculated using the formulas noted below:

```
duration in days = date2 - date1 + 1
```

- **Months** A duration expressed in months is calculated using the INTCK function of SAS as follows: months=intck('month','date1'd,date2'd, 'continuous').
- Years A duration expressed in years between one date (date1) and another later date (date2) is calculated as follows:
 - duration in years = intck('year', 'date1'd, 'date2'd, 'continuous').
- Age Age at time of informed consent, reported on the CRF
- **Height** Height entries made in inches (in) are converted to centimeters (cm) using the following formula:
 - height (cm) = height (in) \times 2.54.
- Weight Weight entries made in pounds (lb) are converted to kilograms (kg) using the following formula:
 - weight (kg) = weight (lb)/2.2046.
- **Temperature** Temperature entries in degrees Fahrenheit are converted to degrees centigrade using the following formula:
 - temp (degrees centigrade) = $5/9 \times [\text{temp (degrees Fahrenheit)} 32].$

- Body Mass Index (BMI) BMI is calculated using height (cm) and weight (kg) using the following formula:
 BMI (kg/m²) = weight (kg)/ [[height (cm)/100]²].
- **Change from baseline** Change from baseline will be calculated as: Change = post-baseline value baseline value.
- **Percent change from baseline** Percent change from baseline will be calculated as: Percent change from baseline = (post-baseline value baseline value)/baseline value × 100.

APPENDIX B: SAS PROGRAMMING QC REQUIREMENTS

Derived datasets are independently reprogrammed by a second programmer. The separate datasets produced by the 2 programmers must match 100%. Detailed specifications for the derived datasets are documented in the study Analysis Dataset (ADaM) Specifications provided to Dermavant at study conclusion.

[figure not shown]
Tables are independently reprogrammed by a second programmer for numeric results.

Listings are checked for consistency against corresponding tables, figures, and derived datasets.

Figures are checked for consistency against corresponding tables and listings, or independently reprogrammed if there are no corresponding tables or listings.

The entire set of TLFs is checked for completeness and consistency prior to its delivery to Dermavant by the lead biostatistician and a senior level, or above, reviewer.

